8.6 Adverse Event analyses

Adverse Events will be analysed descriptively for the Safety population. Implant survival will be analysed and illustrated with a Kaplan-Meier survival curve.

Adverse Events and Serious Adverse Events will be coded with the MedDRA dictionary and tabulated by Preferred Term-code and System Organ Class-code and treatment.

8.6.1 Analyses of Safety variables

All safety variables will be analysed descriptively for the Safety population.

8.7 Analyses of Surgical, Demographics and Baseline variables

The Surgical, Demographics and Baseline variables will be analysed descriptively for the ITT population and PP population.

8.8 Analyses of concomitant medications and treatments

Concomitant medications will be coded and tabulated by treatment.

8.9 Interim analysis

No interim analyses are planned. In addition to the main analysis at 6 months, only a follow-up analysis after 24 months is planned.

8.10 Statistical Analysis Plan

A statistical analysis plan (SAP) with detailed statistical analyses specified for all variables and time points will be written and signed before the database lock.

9 Administrative Aspects

9.1 Training

The Sponsor will organise an initiation visit before study start. The visit will cover: the CIP, investigational procedures including the informed consent process, instructions regarding CRF completion and any other matters or queries related to running the investigation at the site.

The principal investigator will ensure that appropriate training relevant to the investigation is given to the medical, nursing and other staff involved at the clinic and that new information of relevance to the performance of this investigation is forwarded to the staff involved.

9.2 Investigational data

9.2.1 Case Report Form (CRF)

Data Collection will be done by using a paper document (pCRF) or electronic system (eCRF) for each subject on which information will be reported. Specific instructions on how to complete the CRF will be provided to the investigator and other site staff. Completed CRFs will be reviewed and signed by an investigator.

9.2.2 Source data

Source data is defined as all the information in original records, certified copies of original records of clinical findings, observations, or other activities in a clinical investigation, necessary for the reconstruction and evaluation of the clinical investigation.

The CRF could be source data and before the initiation of the investigation the principal investigators should together with the monitor complete the template 'Origin of source data' stipulating where source data should be recorded at the investigational site.

9.2.3 Data management

A data management plan will be written that describes the overall data handling process including data validation, clarification of data and the clean file process.

The database management system iDataFax will be used. It will allow automated CRF tracing, facilitate data entry, provide easy data export into SAS and to Sponsor. It meets all the FDA (21 CFR§11) and ICH requirements.

All outstanding questions regarding data should be handled during the clean file meeting. After declaring clean file the data will be locked.

9.3 Archiving

The Sponsor and principal investigator shall maintain the investigation documents as required by the applicable regulatory requirements.

9.4 Device accountability

Access to the devices used in the investigation shall be controlled and the devices shall be used according to this CIP.

The principal investigator or authorised designee shall keep records documenting the device identity (batch number/serial number or unique code), use of the device and disposal of the device (if applicable) in accordance with standard procedures at the hospital and in accordance with local regulations.

9.5 Quality control

9.5.1 Monitoring

The Sponsor will appoint a monitor that will visit sites during the investigation. The monitor will be appropriately trained and informed about the nature of the investigation, ISO 14155:2011 and applicable regulatory requirements.

The monitor will verify the informed consent of participating subject, that the investigational team is adhering to the protocol and that data are accurately recorded in the CRF.

The monitor must have direct access to source data.

9.5.2 Audit

Audits of the clinical investigation may be conducted by the Sponsor or third party designated by the Sponsor to evaluate compliance with the CIP, written procedures, ISO-14155:2011 and applicable regulatory requirements.

9.6 Clinical Investigation Plan

9.6.1 Deviations from Clinical Investigation Plan

Any deviation from the CIP will be recorded together with an explanation of the deviation. Deviations will be reported to the Sponsor, who is responsible for analysing them and assessing their

significance. The appropriate ethics committee/institutional review board and regulatory authorities (if applicable) will be informed of any significant protocol deviations.

9.7 Suspension or premature termination

The Sponsor may suspend or prematurely terminate either an individual investigation site or the entire clinical investigation for significant and documented reasons. A principal investigator may suspend or prematurely terminate participation in the clinical investigation at the investigational site for which he/she is responsible.

9.8 Publication policy

The result of this study will be published. Authors of the primary publication based on this study must fulfil the criteria defined by the International Committee of Medical Journal Editors (ICMJE).

The primary publication must be published before any secondary publications are submitted for publication.

1 STUDY DETAILS

1.1 Study Objectives

1.1.1 Primary objective

To compare the hearing performance with the Baha Attract System (aided) and the unaided hearing performance.

1.1.2 Secondary objectives

- To compare the hearing performance with the Baha Attract System and the hearing performance with the same sound processor on a Baha Softband.
- To compare health status, health-related quality of life and utility scores before and after use of the Baha Attract System.
- To compare the self-reported assessment of hearing aid outcome before and after use of the Baha Attract System.
- To collect surgical information.
- To investigate if the Sound Processor Magnet strength and magnetic force required for retention changes over time.
- To collect information regarding pain, discomfort, numbness and soft tissue status.
- To monitor implant survival.
- To collect Adverse Events and device deficiencies.

1.2 Study Design

This investigation is a multicentre, open, prospective clinical investigation with only one device group. It is a 6 months investigation with an 18 months follow-up period.

Protocol:
Post-market clinical follow-up of a magnetic bone conduction implant

Protocol No:
CBAS5477

Version:
 1.0

Page 6 of 18

1.2.1 Flowchart

Procedures and timing	Visit 1 Softband test	Visit 2 Surgery	Visit 3 Suture removal	Visit 4 Fitting	Visit 5	Visit 6	Visit 7	Visit 8 *	Visit 9 *
Day/Week/Month ¹	Pre-op	D 0	D 10	W 4	W 6	W 12	M 6	M 12	M 24
Time window			± 5d	± 1w	± 1w	± 2w	± 4w	± 4w	± 4w
Demographics	X								
Medical history	X								
Nicotine use	X								
Audiogram ²	X								X
Eligibility criteria	X								
Informed consent	X								
Soft tissue thickness	X or X								
Health Utility Index (HUI) ³	X ⁴						X		X
Abbreviated Profile of Hearing Aid Benefit (APHAB) ³	X ^{4,5}						X ⁶		X ⁶
The Speech, Spatial and Qualities of Hearing Scale (SSQ) ³	X ^{4,5}						X ⁶		X ⁶
BC Direct using BFS	X ⁷			X ⁸					X ⁹
Selection of sound processor	X								
Change of sound processor				X ⁹	X ⁹	X ⁹	X ⁹	X ⁹	X ⁹
Fitting of sound processor	X ⁷			X ⁸					X ⁹
Fine tuning of sound processor					X ⁹	X ⁹	X ⁹	X ⁹	X ⁹
Free field thresholds	X ^{5,7}			X ⁸			X ⁸	X ⁸	X ⁸
Speech recognition in noise	X ^{5,7}			X ⁸			X ⁸	X ⁸	X ⁸
Speech recognition in quiet	X ^{5,7}			X ⁸			X ⁸	X ⁸	X ⁸
Home test of sound processor on Softband	X →								
Surgery		X							
Surgery time		X							
Soft tissue thinning		X							
Bone polishing/removal		X							
Implant stability quotient		X							
Suture removal (if applicable)			X						
SP Magnet selection				X					
Magnetic retention force				X	X	X	X	X	X
Change of SP Magnet					X ⁹	X ⁹	X ⁹	X ⁹	X ⁹
Questions regarding: • Daily use of sound processor • Magnet retention • Change of soft pad					X	X	X	X	X
Pain/discomfort					X	X	X	X	X
Numbness			X	X	X	X	X	X	X
Soft tissue status			X	X	X	X	X	X	X
Loss/removal of Implant or Implant Magnet			X	X	X	X	X	X	X

STATISTISKA KONSULTGRUPPEN		Statistical Analysis Plan	
Protocol: Post-market clinical follow-up of a magnetic bone conduction implant		Protocol No: CBAS5477	
		Version: 1.0	Page 7 of 18

Device deficiency		X	X	X	X	X	X	X	X
Adverse Events		X	X	X	X	X	X	X	X
Concomitant medication/treatment	X	X	X	X	X	X	X	X	X
Extra visit									
Extra visit									

¹ The time between visits was calculated from Visit 2 (time 0); ² Only if the last audiogram that was performed on the subject was older than 6 months; ³ To be completed by the subject; ⁴ Before Softband test; ⁵ Unaided; ⁶ Aided; ⁷ With sound processor on Softband; ⁸ With Baha Attract System; ⁹ If needed; * Visit 8 and 9 are not included in the sixth months analysis

1.3 Device/Treatment Groups

Only one device group is included in this study.

1.4 Sample Size

1.4.1 Sample size calculation for the primary efficacy analysis:

In order to achieve 90 % power to detect a clinically significant difference of 10 dB in free-field hearing thresholds between the unaided situation and the Baha Attract System at the 6 months visit with Fisher's non-parametric permutation test for paired observation, two-sided test with significance level 0.05, on the ITT population 20 evaluable subjects are needed assuming a within subject standard deviation (SD) of 13.0 dB. The within subject SD for change in PTA4 has been estimated to 12.3 dB in a previous study within Cochlear comparing unaided hearing with a BP100 sound processor on a Cochlear Baha Attract System, CBAS5477 42 (51) Softband versus unaided hearing. To compensate for a 10% drop out rate in the study 22 subjects should be included in the investigation.

1.4.2 Sample size calculation for the for the secondary analysis

In order to achieve 90 % power to detect a clinically significant change of 1.5 dB in free-field hearing thresholds from Softband to the Baha Attract System at the 6 months visit with Fisher's non-parametric permutation test for paired observation, two-sided test with significance level 0.05, on the ITT population 46 evaluable subjects are needed assuming a within subject SD of 3 dB. The within subject SD for change in PTA4 has been estimated to 2.89 dB in a previous study within Cochlear comparing outcomes with a BP100 sound processor on a Softband versus on an abutment.

1.4.3 Overall sample size considerations

In order to achieve 90% power both for the primary analysis (PTA4, Baha Attract vs. unaided) and the secondary analysis of the primary variable (PTA4, Baha Attract vs. Softband), 46 evaluable subjects are needed. To compensate for a 10% drop out rate in the study 52 subjects will be included in the investigation.

2 STUDY POPULATIONS

2.1 Definition of Study Populations

The final definition of the analysis sets (ITT, PP and Safety) will be taken at the clean file meeting before database lock.

Protocol:

Post-market clinical follow-up of a magnetic bone conduction implant

Protocol No:

CBAS5477

Version:

1.0

Page 8 of 18

2.1.1 *Intent-to-Treat Population (Full Analysis Set)*

The Intention-to-Treat population (ITT) will include all subjects who have received the surgical intervention.

2.1.2 *Per-Protocol Population*

The Per Protocol population (PP) will include subjects that have completed the investigation according to the protocol. Subjects that were incorrectly included or were considered major protocol violators should be removed from the PP population.

2.1.3 *Safety Population*

The Safety population consists of all surgically treated subjects

3 STUDY VARIABLES

3.1 Baseline and pre operation variables

3.1.1 *Demographics and Baseline Characteristics*

- Age (years), calculated from date of birth and date of
- Gender
 - Male
 - female
- Ethnicity
 - American Indian/Alaska Native,
 - Asian,
 - Black or African American,
 - Native Hawaiian/Pacific Islander,
 - White,
 - Other
- Weight (kg), (convert lbs to kg)
- Height (cm), (convert in to cm)
- Nicotine use
 - Subject does not smoke
 - <= 10cig/day
 - 11-20 cig/day
 - 21-40 cig/day
 - > 40 cig/day
- Site
 - Nijmegen, Netherlands
 - Manchester, UK
 - Birmingham, UK
 - Milwaukee, USA
 - Kajetany, PL
- Country
 - Netherlands
 - UK
 - USA
 - Poland

3.1.2 *Pre operation variables*

- Treatment ear

Protocol:

Post-market clinical follow-up of a magnetic bone conduction implant

Protocol No:

CBAS5477

Version:

1.0

Page 9 of 18

- Right
- Left
- Type of hearing loss
 - Conductive/mixed
 - SSD
- Aetiology
 - (Chronic) Infection
 - Tumour
 - Trauma
 - Malformation
 - Otosclerosis
 - Other
- Current hearing aid
 - Yes
 - No
- Selection of sound processor
 - Baha BP110
 - Baha 4
 - Baha 5

3.1.3 Audiogram

Audiogram at Visit 1, Air condition/Bone conduction, Right/Left (transferred to Baha side/Non Baha side), Unmasked/Masked for 250, 500, 750, 1000, 1500, 2000, 3000, 4000, 6000 and 8000 Hz.

3.1.4 Medical and Surgical History

- Medical history will be coded using MedDRA 18.0.
- Surgical history will be coded using MedDRA 18.0.

3.1.5 Prior and Concomitant Medications

Prior medication is medication that has been used between Visit 1 and Surgery. Concomitant medications is medications used after surgery to end of study. Medications are coded according to WHO CC ATC.

3.1.6 Concomitant Treatments/Procedures

Concomitant Treatments/Procedures between Visit 1 and end of study will be collected. These terms will not be coded.

3.2 Efficacy Variables

3.2.1 Primary Efficacy Variable

Threshold audiometry: PTA4 (mean of 500, 1000, 2000 and 4000Hz)

3.2.2 Secondary Efficacy Variables

- Thresholds audiometry: 250, 500, 1000, 2000, 3000, 4000, and 6000 Hz at visit 1, w 4, m 6, m 12 and m 24.
- Adaptive speech recognition in noise (50% performance) at visit 1, w 4, m 6, m 12 and m 24.

Protocol:

Post-market clinical follow-up of a magnetic bone conduction implant

Protocol No:

CBAS5477

Version:

1.0

Page 10 of
18

- Speech perception in quiet (50dB, 65dB and 80dB SPL) at visit 1, w 4, m 6, m 12 and m 24.
- BC Direct thresholds at visit 1 and w 4
- Generic quality of life scale: Health Utility Index (HUI):
 - Health related quality of life score for overall health
 - Vision score
 - Hearing score
 - Speech score
 - Ambulation/mobility score
 - Dexterity score
 - Self-care score
 - Emotion score
 - Cognition score
- Abbreviated Profile of Hearing Aid Benefit (APHAB):
 - Ease of Communication
 - Reverberation
 - Background Noise
 - Aversiveness
 - Global score
- The Speech, Spatial and Qualities of Hearing Scale (SSQ)

Surgical variables

- Soft tissue thickness (mm)
- Surgery time (time of first incision to time of last suture), (min)
- Soft tissue thinning performed
 - Yes
 - No
- Bone polishing/removal performed
 - Yes
 - No
- ISQ Low
- ISQ High
- BI300 length
 - 3 mm
 - 4 mm

Questions regarding Sound processor magnet by visit and changes over time (w 4, w 6, w 12, m 6, m 12 and m24)

- Choice of SP Magnet (SPM1 (weakest), SPM2, SPM3, SPM4, SPM5, SPM6 (strongest))
- Mean Magnetic retention force (mean of three values). If there is large variations within the three measurements median of the three values will be used instead.

Questions about usage will be collected for w 6, w 12, m 6, m 12 and m24:

- Daily use of SP (hours/day)
- Number of times SP fell off during last week
- Number of times SP fell off during last week per Daily use (times/hours/day)
- Number of Soft pad changes per week (calculated from changes last week and changes last month)
- Number of Soft pad changes per Daily use (changes/hours/day)

Protocol:

Post-market clinical follow-up of a magnetic bone conduction implant

Protocol No:

CBAS5477

Version:

1.0

Page 11 of
18

3.3 Safety Variables

3.3.1 Adverse Events

Treatment emergent adverse events will be presented. Treatment emergent is defined as an event happening at or after surgery. Three predefined AE categories (Magnetic retention difficulties, Pressure related skin complications, Pain/Discomfort) will be used, and if other is checked those will be MedDRA (version 18.0) coded.

- Adverse Event (AE) is all reported events
- Adverse Device Effect (ADE) is events that is Related to the device (Probably) or Related to the procedure (Probably)
- Serious Adverse Event (SAE) is events that has been marked as Serious
- Serious Adverse Device Effect (SADE) is events that has been marked as Serious and also marked as Related to the device (Probably) or Related to the procedure (Probably)

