6.23 Soft tissue status

At Visit 3-9, the investigator will examine the soft tissue at the implant site. In case of signs of e.g. inflammation, infection, skin necrosis or scar hypertrophy, the event shall be reported on the Adverse Event page in the CRF. If any treatment is provided, it shall also be recorded on the Concomitant medication page in the CRF.

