7.2 Residual risks associated with the device and procedures

Risks associated with the transcutaneous coupling that cannot be completely eliminated include magnetic retention difficulties, pressure-related skin complications and pain/discomfort. The system has been designed to minimise these risks. For example:

- The SP Magnet has been designed with a Soft pad on the soft tissue facing surface to evenly distribute the pressure, thus minimising the occurrence of peak pressure areas.
- To minimise the risk of pressure-related complications, the transcutaneous coupling has been designed such that the average pressure over the skin should not exceed 0.4 N/cm² (capillary blood pressure) and peak pressures should not exceed 0.6 N/cm² (diastolic blood pressure).
- The surgeons are instructed to carefully thin the soft tissue flap during surgery if the skin thickness exceeds 6 mm, to ensure good magnetic retention.
- Subjects with a soft tissue flap thickness of less than 3 mm are not included in the investigation.
- Sound processor loading shall be performed at 4 weeks post surgery. However, if the wound is not sufficiently healed, loading should be delayed.
- The investigators and the subjects will be instructed to carefully select an appropriate SP Magnet by balancing the magnet retention to avoid any skin problems.

The surgical procedure associated with the Baha Attract System is described in the Surgery Guide for the Baha Attract System. The guide has been developed by the Sponsor together with a group of experienced Baha surgeons.

Tests have demonstrated that the Implant Magnet in combination with the BI300 Implant is MRI conditional for up to 1.5 Tesla. Subjects that receive the Baha Attract System will receive an MRI card, for use by radiologists to evaluate and plan any MRI examination. Subjects that have received radiation therapy at the same side of the skull where the Baha Attract will be positioned are excluded from the investigation.

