6 CHANGES OF ANALYSIS FROM PROTOCOL

No changes of the analyses according to the protocol are made.

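### SAP 3.3.1 provides MedDRA coding only for adverse events ticked as *other*, so the three named device risks get no SOC/PT breakdown, an undeclared departure from protocol 8.6

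*SAP*

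**What the plan says.** Protocol 8.6 gives one rule for all events: "Adverse Events and Serious Adverse Events will be coded with the MedDRA dictionary and tabulated by Preferred Term-code and System Organ Class-code and treatment". It exempts no class of event.

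SAP 3.3.1 describes a different scheme. First, "Three predefined AE categories (Magnetic retention difficulties, Pressure related skin complications, Pain/Discomfort) will be used". Then, for whatever does not fit, "if other is checked those will be MedDRA (version 18.0) coded". Nothing is said about coding events that go into the three boxes. The same section defines the reporting unit broadly: "Adverse Event (AE) is all reported events".

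SAP 4.11.1 plans summaries of AEs, SAEs, ADEs and SADEs by predefined category, SOC and PT, with numbers of events and of subjects. Tables 14.3.1.2 to 14.3.1.5 in SAP 7.1 have matching titles.

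The three boxes match the list in protocol 7.2 of risks from the transcutaneous coupling that cannot be fully eliminated: "magnetic retention difficulties, pressure-related skin complications and pain/discomfort".

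SAP section 6 states: "No changes of the analyses according to the protocol are made".

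**The concern.** The two documents give different coding rules, and the difference falls on the events the sponsor itself singles out as the remaining risks of the device. Mid- to long-term safety is one of the two aims in protocol 1.2, and soft tissue status and adverse events are both secondary objectives in protocol 1.3.2.

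Two things are at stake. The first is detail: a transient redness and a skin necrosis, if both are ticked as pressure-related skin complications, fall into one row with nothing to tell them apart. The second is the meaning of the SOC/PT counts. A reader who looks up skin or pain terms will normally take the count as complete. Under SAP 3.3.1 it would be only the remainder after the boxed events are taken out.

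**Working it through.** No arithmetic in the plan needs reproducing. The check is a comparison of the relevant sections.

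1. **Coding rule.** Protocol 8.6 covers AEs and SAEs without exception. SAP 3.3.1 attaches coding to the condition that *other* is ticked. The SAP does not say outright that boxed events stay uncoded, but that is the natural reading of the condition. The layout in SAP 4.11.1, where the predefined category is a display level beside SOC and PT, supports it.

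2. **Are boxed events still reported?** Yes. An AE is any reported event (SAP 3.3.1), and the predefined categories are named in the summaries (SAP 4.11.1) and in the titles of Tables 14.3.1.2 to 14.3.1.5. What they lack is a SOC and a PT.

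3. **Effect on SOC/PT counts.** Let *n* be the number of skin (or pain) events and *p* the share ticked in a predefined box. The SOC/PT rows then show *n* × (1 − *p*). The documents give neither *n* nor *p*, so the shortfall can lie anywhere from none (*p* = 0) to all of them (*p* = 1). Event counts could be restored by adding the category row. Subject counts could not, because a subject with both a boxed event and a coded event would be counted twice.

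4. **Can other planned output restore the lost detail?**
   - *Skin.* Protocol 6.23 sends findings to the AE form: in case of signs such as "inflammation, infection, skin necrosis or scar hypertrophy, the event shall be reported on the Adverse Event page". The separate soft tissue variable in SAP 3.3.3 is a single yes/no item covering all four findings, so it cannot tell necrosis from inflammation.
   - *Severity.* Protocol 6.27.2 has each AE graded mild, moderate or severe, but SAP 4.11.1 plans no table by severity.
   - *Seriousness.* SAEs and SADEs have their own tables, which separates serious from non-serious events. Those tables use the same layout, so a boxed SAE also has no PT.
   - *Pain.* SAP 3.3.2 has a four-level scale presented by visit, so the loss is smaller here.
   - *Retention.* SAP 3.2.2 counts how often the processor fell off, so again the loss is smaller.
   - *Listings.* SAP 7.3 leaves these to be decided elsewhere, so the plan does not guarantee them.

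5. **Declaration.** SAP section 6 reports no change, so the departure is neither stated nor justified.

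The contradiction stands, and its main practical consequence is for skin events.

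**The case against.** A reader might infer that the AE tables leave out the device-related events, or that safety data go missing. The documents do not support that. Every reported event counts as an AE, and each predefined category is shown with events and subjects in the same tables as the coded terms.

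A reader might also infer that all four soft tissue findings in protocol 6.23 collapse into one row. That is possible but not shown. An infection or a hypertrophic scar need not be pressure related; if ticked as *other*, it would be coded. The AE form and its completion instructions are not in the documents, so inconsistent ticking between sites is likewise a possibility and not a finding.

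Nor can the effect be sized from the visit schedule. Soft tissue is examined at Visits 3 to 9, and 7 visits × 52 subjects = 364, but that counts scheduled examinations, not events.

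It is also fair to say that the SAP is silent, not explicit, on coding boxed events; that this is a single-arm study with descriptive safety analysis; and that pain, retention failures and implant or magnet loss have their own outputs.

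These points limit the concern without removing it. Protocol 8.6 requires a SOC/PT breakdown for all events, the SAP provides it for only some, and no other planned table separates the types of skin event within a category.

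**Conclusion.** The SAP departs from the protocol's coding rule for the three named device risks and does not declare it. Events in those categories are counted but shown only as undivided rows. SOC/PT counts describe the *other* events alone and are too low for skin and pain whenever a box is used. Detail within a category is lost, most clearly for skin.

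This rests on reading SAP 3.3.1 to mean that boxed events are not coded. How far the counts are understated depends on how many events occur and how they are ticked, neither of which the documents give. The primary analysis and the sample size are unaffected. This is a correctable inconsistency in safety reporting that changes the content of the safety tables, so it should be fixed.

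**What to change.** In SAP 3.3.1, state that every AE and SAE is MedDRA coded, including those in the predefined categories, and in SAP 4.11.1 that all of them are tabulated by SOC and PT as protocol 8.6 requires. Keep the predefined-category rows already planned for Tables 14.3.1.2 to 14.3.1.5 as an additional grouping, with a footnote that those events also appear under their SOC and PT, so that no one adds the two.

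The cost is coding some extra terms and a small change to the table shells. MedDRA 18.0 is already in use for *other* events and for medical and surgical history (SAP 3.1.4). Coding depends on a description of the event in the CRF. The documents do not show whether one is collected for boxed events, so code from it where it exists and report how many events have none.

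If the sponsor prefers the current scheme, SAP section 6 must declare the departure from protocol 8.6 and justify it, and the table titles or footnotes should say that the SOC/PT rows exclude the predefined categories.

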6.27 Adverse Event (AE) and Serious Adverse Event (SAE)

6.27.1 Definitions

Term	Definition
Adverse Event (AE)	Any untoward medical occurrence, unintended disease or injury, or untoward clinical signs (including abnormal laboratory findings) in subjects, users or other persons, whether or not related to the medical device used in the investigation*. This definition includes events related to the procedures involved.
Adverse Device Effect (ADE)	Adverse event related to the use of medical device used in the investigation*. 
 • This definition includes adverse events resulting from insufficient or inadequate instructions for use, deployment, implantation, installation, or operation, or any malfunction of the investigational medical device. • This definition includes any event resulting from use error or from intentional misuse of the investigational medical device.
Serious Adverse Event (SAE)	A SAE** is an adverse event that: 
 • results in death • is life-threatening • requires inpatient hospitalisation or prolongation of existing hospitalisation • results in persistent or significant disability/incapacity • is a congenital anomaly/birth defect • has led to a important medical event that may have jeopardised the subject or may have required an intervention to prevent one of the above characteristics/ consequences. These can include complaints that might have led to a medical occurrence if 
 ○ suitable action had not been taken or ○ intervention had not been made or ○ if circumstances had been less fortunate. 
NOTE: Planned hospitalization for a pre-existing condition, or a procedure required by the CIP, without serious deterioration in health, is not considered a serious adverse event.

Serious Adverse Device Effect (SADE)	Adverse device effect that has resulted in any of the consequences characteristic of a serious Adverse Event
Unanticipated Serious	Serious adverse device effect which by its nature, incidence, severity or

Adverse Device Effect (USADE)	outcome has not been identified in the current version of the risk analysis report
Device deficiency	Inadequacy of a medical device with respect to its identity, quality, durability, reliability, safety or performance NOTE Device deficiencies include malfunctions, use errors, and inadequate labelling.

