6.27.2 Handling and reporting of AEs

Subjects will be carefully monitored during the investigation for possible AEs and appropriate treatment of the subject will be initiated.

Any AE observed will be fully investigated by the investigator and documented in the case report form (CRF) including assessment of severity (mild, moderate or severe) and relationship to the medical device.

6.27.3 Reporting of SAEs and device deficiency that could have lead to a SAE

An investigator should report within 24 hours, after being aware of the event, an SAE or a device deficiency that could have lead to a SAE. The report should be sent as an e-mail attachment to Cochlear Bone Anchored Solutions AB. Instructions and contact information is available on the SAE form.

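### SAP 3.3.1 admits events marked only as procedure-related to the ADE and SADE counts, which goes beyond the protocol's device-based definition, with no split planned and no change declared

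*SAP*

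**What the plan says.** **Protocol.** Section 6.27.1 defines an ADE as "Adverse event related to the use of medical device used in the investigation". Two sub-points widen this. One covers events arising from "insufficient or inadequate instructions for use, deployment, implantation, installation, or operation, or any malfunction of the investigational medical device". The other reads "This definition includes any event resulting from use error or from intentional misuse of the investigational medical device". A SADE is an "Adverse device effect that has resulted in any of the consequences characteristic of a serious Adverse Event", so it inherits the link to the device. Procedures in general appear only in the AE entry of the same table: "This definition includes events related to the procedures involved". Section 6.27.2 asks the investigator for "assessment of severity (mild, moderate or severe) and relationship to the medical device" and does not mention a separate judgement about the procedure. Section 5.2.3 lists ADEs and SADEs among the safety variables, and section 8.6.1 has them analysed descriptively.

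**SAP.** Section 3.3.1 works from two marks, one for the device and one for the procedure, and either is enough: "Adverse Device Effect (ADE) is events that is Related to the device (Probably) or Related to the procedure (Probably". A SADE is an event "marked as Serious and also marked as Related to the device (Probably) or Related to the procedure (Probably". These categories feed the overview and the summaries in section 4.11.1, which are Tables 14.3.1.1, 14.3.1.3 and 14.3.1.5 in section 7.1. Section 6 states that the analyses do not change from the protocol. Section 7.3 leaves the listings to be decided elsewhere.

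**The concern.** Under the SAP rule, an event that the investigator marks as related to the procedure and not to the device is still tabulated as a device effect. The ADE and SADE summaries are the only planned outputs that attribute events to the device by causality. The predefined AE categories in SAP 3.3.1 describe the type of event, not its cause.

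The situation can plausibly arise. Everyone in the Safety population has had surgery, under general or local anaesthesia (Protocol 6.16), and adverse events count from surgery onwards. The soft tissue is first examined at the day 10 visit, whereas the sound processor is fitted at week 4 (Protocol 6.18). A reader who applies the protocol definition to these tables could take surgical events for device effects. Because SAP section 6 records no change, nothing would warn that reader.

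**Working it through.** The plan gives no figure to reproduce, so the check compares the definitions.

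**Step 1: the four possible markings.** Let D be the events marked device-related and P the events marked procedure-related, both at the grade that the SAP uses.

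| Device mark | Procedure mark | SAP 3.3.1 | Protocol 6.27.1 |
|---|---|---|---|
| yes | yes | ADE | ADE |
| yes | no | ADE | ADE |
| no | yes | ADE | ADE only if one of the widening routes applies |
| no | no | not an ADE | not an ADE on these marks |

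The definitions part in the third row. For serious events the same table gives SADE.

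**Step 2: size at a fixed grade.** The SAP counts events in D or P. The device-marked count is D. The difference is the number of events in P and not in D, which is zero or more. Neither document gives this number. As a scale only: if all 52 planned subjects are operated on, each subject whose only qualifying event is procedure-only adds 1/52 = 1.9 percentage points to the share of subjects with an ADE. An assumed 1 to 10 such subjects would add 1.9 to 19.2 points (10/52 = 19.2%). These are not expected values.

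**Step 3: direction against the protocol.** The difference in step 2 is measured against D, not against the protocol count. Two things separate D from the protocol count:
- Some procedure-only events may be ADEs under the protocol's widening routes.
- The SAP requires the grade 'Probably', whereas the protocol says only that the event is related. If the CRF has another positive grade, the SAP also leaves out some events that the protocol would count.

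So SAP count minus protocol count = (procedure-only events that meet no protocol route) − (protocol ADEs that the SAP's grade rule leaves out). The first term can only raise the SAP count and the second can only lower it. Neither can be evaluated from the documents.

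**Step 4: outputs affected.** Section 4.11.1 plans four overview rows (AE, SAE, ADE, SADE), and 2 of the 4 use the broader rule. Of the four detailed tables (14.3.1.2 to 14.3.1.5), 2 of 4 use it: 14.3.1.3 and 14.3.1.5. Of the five tables 14.3.1.1 to 14.3.1.5, 0 show procedure-only events separately. A listing could do so, but none is planned in the SAP.

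**The case against.** **The protocol's ADE definition already reaches surgery.** The wording on inadequate instructions can also be read as covering inadequate deployment, implantation or installation in themselves. Two parts of the tested device are placed surgically (Protocol 3.1), so some procedure-marked events may be ADEs under the protocol. This stands, and it makes the boundary less sharp than a plain device-versus-procedure contrast. It does not close the gap. The wording concerns inadequacy, and an anaesthetic event with no link to the device meets none of the routes.

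**A device-only filter would not reproduce the protocol count.** This also stands. The documents show only two marks, and no field identifies the protocol's widening routes. Dropping every procedure-only event could remove a true protocol ADE.

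**The section 6 statement concerns analyses, and these remain descriptive.** Protocol 8.10 leaves detail to the SAP, so turning CRF marks into categories could be seen as such detail. That is arguable. Even so, widening the definition of a named safety variable should be disclosed.

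**The rule is cautious, and nothing is hidden.** The procedure limb on its own can only add events, all events stay in the AE and SAE tables, and the breakdown by system organ class and preferred term shows their nature. This limits the importance of the point. It does not restore the causal attribution that the ADE and SADE tables are meant to give.

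A reader might also infer that reporting to ethics committees is compromised. The documents do not support that. Investigators report every SAE to the sponsor within 24 hours (Protocol 6.27.3), and section 6.27.4 sends SAEs as well as SADEs to committees under local requirements. Neither step depends on how the SAP tabulates events.

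**Conclusion.** The point holds as a minor one. The SAP's ADE and SADE categories admit events marked only as procedure-related, the protocol's definitions do not cover all such events, no planned table separates them, and the SAP declares no change. The consequence is that two overview rows and two detailed tables cannot be read as device attribution in the protocol's sense.

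It would be tempting to say that the SAP overstates device-related harm. The documents do not show this. The number of procedure-only events is unknown and may be zero, and the net direction depends on relatedness grades in a CRF that is not among the documents. AE and SAE totals, efficacy tests and expedited reporting are unaffected. The verdict assumes that the CRF records the two marks separately, as SAP 3.3.1 implies.

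**What to change.** - In Tables 14.3.1.1, 14.3.1.3 and 14.3.1.5, show two separate counts, for all events and for serious events: device-related (with or without a procedure mark) and procedure-only. The two marks that SAP 3.3.1 already uses are enough for this. Event counts will add up. Subject counts may not, because one subject can have both kinds of event.
- Reserve the ADE and SADE labels for events that meet Protocol 6.27.1. Check procedure-only events against its inadequate-implantation, malfunction and use-error routes at the clean file meeting, and do not drop them by a filter.
- If the sponsor keeps the broader definition, record it as a change in SAP section 6 and keep the split.
- As a clarification, state the CRF relatedness grades and which of them count as related.

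The cost is a few lines of SAP text, extra rows in existing tables, and a review of the procedure-only events at a meeting that is already planned. The device-related counts may be lower than the combined counts.
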